3.1.5. Follow-up Period

During the follow-up period, subjects will continue to be monitored for safety. Subjects whose most recent 24-hr UFC is \leq ULN will have a follow-up visit (Visit F1/End-of-Study, EoS; this is the same as the end of trial) at the study site 2 weeks after their ET/EoT visit. Subjects whose most recent 24-hr UFC is $>$ ULN will have a follow-up telephone visit instead of a study site visit.

- Study Days 86-98: If the Day 79 24-hr UFC is \leq ULN, a follow-up visit (Visit F1) at the study site will be scheduled for Day 98, 2 weeks after the EoT visit. This visit will consist largely of safety assessments. Subjects whose Day 84 24-hr UFC is also \leq ULN will begin a 24-hr urine collection on Day 92 and finish on Day 93. If the Day 79, Day 84 or Day 92 24-hr UFC is $>$ ULN, a telephone visit will be conducted on Day 98 instead of a study site visit (in case of discrepant results, the latest result should be used). If the Day 92 24-hr UFC result is unknown at the time the Day 98 visit is due, the subject will proceed with having the Day 98 visit at the study site.
- Subjects whose Day 92 24-hr UFC is \leq ULN should continue to be followed up and have morning serum ACTH and 24-hr UFC assessed every 2-4 weeks until their 24-hr UFC is $>$ ULN or until the Investigator and the Medical Monitor agree that the subject is stable.

Throughout the course of the study, safety evaluations will include assessment of AEs, concomitant medications, clinical laboratory tests, vital signs, physical examinations (PEs) and 12-lead electrocardiograms (ECGs).

A detailed schedule of study assessments is presented in [Appendix 1](#).

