6.10.1. Efficacy Assessments

6.10.1.1. 24-Hour Urinary Free Cortisol

24-hr urine collections for assessment of UFC will be performed using the standard procedure (see Laboratory Manual). If a urine collection is suspected to be incomplete, a repeat 24-hr UFC may be performed with approval of the Medical Monitor.

Two collections will be done during the screening period, within 28 days prior to enrollment into the open-label dose-escalation period (Visit T1), and results reviewed for eligibility prior to enrollment. Subjects who require wash-out of medications should perform these collections AFTER wash-out.

During the Open-Label Dose-Escalation Period of the study, subjects will begin a 24-hr urine collection on Days 13, 14, 27, 28, 41, 42, 50, 51, and 56. In addition, subjects in the Double-Blind Randomized Withdrawal Period of the study will begin a 24-hr urine collection on Days 64, 65, 79, and 84; and subjects in the Additional Open-Label Dosing Period of the study will begin a 24-hr urine collection on Days 69, 70, 79, and 84. The collections that occur within 2 days before study visits should be brought to the corresponding study visit (along with any other samples that had not been previously submitted). For all other collections, when completed, a visiting nurse may assist with processing and shipping these 24-hr collections to the central laboratory, or the subject may submit them to the study site, per subject preference.

The mean of the Day 50 and the Day 51 (“mean Day 50/51”) 24-hr UFC results will be used by the Investigator to determine whether the subject meets criteria for randomization. For subjects in the Double-Blind Randomized Withdrawal Period of the study, the mean of the Day 64 and the Day 65 (“mean Day 64/65”) 24-hr UFC results, if available at the time of Visit R2, will be used by the Investigator to determine whether the subject should undergo Visit R3 rather than Visit R2. The Day 79 result and the Day 84 result will be used to make the initial determinations of whether the subject’s follow-up visit should be conducted at the study site or via telephone.

In addition, subjects whose Day 84 24-hr UFC is \leq ULN will collect an additional 24-hr urine sample for UFC on Day 92. This result, if available at the time the Day 98 visit is due, will also be used to determine whether the subject’s follow-up visit should be conducted at the study site or via telephone.

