7.3.4. Visit R3 (Day 85; End-of-Treatment)/Early Termination

At Visit R3 (EoT)/ET, appropriate study site personnel should:

- Receive the Day 84 saliva collections and 24-hr urine collection (and any other collections that were not previously submitted) from the subject and submit these to the central laboratory for analysis.
- Record adverse events and update medications.
- Record vital signs and weight.
- Perform a complete PE.
- Obtain a 12-lead ECG.
- Collect fasting blood samples for hematology, chemistry, PT, aPTT, INR, insulin, HbA1c, lipid panel, hormones (11-DOC, 17-OHP, A, A4, ACTH, cortisol, DHEA, DHEAS, free T, P, renin, SHBG and total T) and PK.
 - All blood hormone collections should be performed between 6-10 AM (06:00-10:00), as close to 8 AM (08:00) as practicable.
 - Subjects need to be in a seated position for at least 15 minutes prior to collection of blood hormone levels so that renin and aldosterone levels are stable.
 - If the subject is not fasting, proceed with the visit but mark the sample collection as being non-fasting.

- Collect a urine sample for urinalysis and, if the subject is a woman of childbearing potential, perform a urine pregnancy test (preferred; or submit a serum or urine sample to a laboratory for pregnancy testing if required by your institution/IRB/EC).
- Record the date and time of the subject's last previous study drug dose (expected to have occurred the evening prior to the visit).
- Collect study drug and assess compliance.
- If the subject's most recent available 24-hr UFC result is \leq ULN, then:
 - A Day 92 24-hr UFC may or may not be needed. Provide instructions regarding a 24-hr urine sample to be collected at home starting in 7 days (Day 92 or R3/ET+7) (Section 7.5.1). If the Day 84 24-hr UFC result is $>$ ULN, inform the subject that they will not need to collect this sample.
 - Schedule the next study visit (Visit F1).
- If the subject's most recent 24-hr UFC is $>$ ULN, follow up with the subject via telephone in 13 days to assess for new AEs. Subjects who have ongoing AEs should be followed up as appropriate. After completing Visit R3/ET, subjects whose most recent 24-hr UFC is $>$ ULN may begin treatment with another agent for Cushing's syndrome at the discretion of their physicians.

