7.5.1. Between Visits R3/A3/ET and F1

At the indicated study days, subjects whose Day 84 24-hr UFC result was \leq ULN should:

- Day 92 (R3/ET+7): Begin a 24-hr urine collection.
- Day 93 (R3/ET+8): Take the 24-hr urine collection to the study site, or a visiting nurse will assist with processing the sample and shipping it to the central laboratory, per subject preference.

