[^] Subjects whose Day 84 24-hr UFC is \leq ULN should collect a repeat 24-hr UFC starting 7 days after R3/A3/ET. If the repeat 24-hr UFC is also \leq ULN, the subject should return for a follow-up visit at the study site 13 days after R3/A3/ET. Only subjects whose most recent 24-hr UFC is \leq ULN need to have a follow-up visit at the study site. Such subjects should continue to be followed up and have morning serum ACTH and 24-hr UFC assessed every 2-4 weeks until their 24-hr UFC is $>$ ULN or until the Investigator and the Medical Monitor agree that the subject is stable. All other subjects should be followed-up via a telephone call (instead of having a follow-up visit at the study site).

^{*} Subjects should take the evening dose of study drug with food the evening prior to study visits during the open-label intra-subject dose-escalation period, the double-blind randomized withdrawal period, and the additional open-label dosing period. On the morning of study visits (except S1, R3/A3/ET and F1), subjects should not take their study drug until directed by study site personnel. Subjects should document the time of their last study drug dose prior to each visit.

[§] Prior to randomization into the double-blind randomized withdrawal period or enrollment into the additional open-label dosing period, subjects should be evaluated for meeting randomization criteria. A subject is eligible to enter the double-blind randomization period if the mean Day 50/51 24-hr UFC is \leq ULN or is \leq 50% of the baseline value. Subjects whose mean Day 50/51 24-hr UFC does not meet either of these criteria are eligible to enter the additional open-label dosing period.

^a Height at screening only.

^b A complete physical examination (PE) will be performed at S1, T1, R1/A1 and R3/A3/ET. A brief PE will be performed at T2, T3, R2/A2 and F1, with particular attention to assessing the subjects for adrenal insufficiency. At all other visits, targeted PEs may be performed if needed based on adverse events and positives from review of systems.

^c Subjects should be fasting after 10 PM (22:00; water and maintenance medications allowed) the evening prior to S1, R1/A1 and R3/A3/ET.

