^d Blood hormone levels to be assessed include 11-DOC, 17-OHP, A, A4, ACTH, cortisol, DHEA, DHEAS, free T, P, renin, SHBG and total T. All blood hormone levels should be drawn in the morning, as close to 8 AM (08:00) as practicable and between the hours of 6-10 AM (06:00-10:00). During the screening period, subjects who require a wash-out of medications that affect cortisol levels should NOT have their hormone levels drawn until they have completed the required wash-out.

^e At each study visit from T1 to R2/A2, a trough PK level will be collected within 30 minutes prior to dosing. At T1, T2, and T3, plasma for PK assessments will then be collected 1, 2, 3 and 4 hours post-dose. At R3/A3/ET, a trough PK level will be collected (no study drug will be dosed).

^f Pregnancy tests will be performed on female subjects of childbearing potential only. A serum pregnancy test will be performed at S1; a urine pregnancy test will be performed at all other visits unless otherwise required by the institution/IRB/EC.

^g Urine drug screen at S1 only for cocaine, amphetamines and opioids.

^h TWO 24-hr urine collections for UFC should be performed during the screening period within 28 days of enrollment into the open-label dose-escalation period and results reviewed for eligibility prior to enrollment. Subjects who require wash-out of medications should perform these collections AFTER wash-out. Subjects whose Day 84 24-hr UFC is \leq ULN will perform a 24-hr urine collection on Day 92. A visiting nurse may assist with processing and shipping the Screening and Day 41, 42, 50, 51, 64 (if applicable), 65 (if applicable), 79, and 92 (if applicable) urine collections to the central laboratory; or the subject may submit these to the study site for shipping to the central laboratory, per subject preference (all other collections should be brought by the subject to the next visit at the study site).

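### The protocol states the rule for the Day 92 safety UFC in two ways, and the exit-visit steps can cancel that collection but cannot add it

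*Protocol*

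**What the plan says.** **Two results required.** In section 3.1.5, and in the same words in the synopsis, the Days 86-98 bullet starts from a Day 79 UFC at or below ULN and schedules an on-site F1. It then says: "Subjects whose Day 84 24-hr UFC is also \leq ULN will begin a 24-hr urine collection on Day 92 and finish on Day 93". The word *also* makes the collection conditional on both results.

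**Day 84 alone required.** Section 7.5.1 says: "At the indicated study days, subjects whose Day 84 24-hr UFC result was \leq ULN should", followed by "Day 92 (R3/ET+7): Begin a 24-hr urine collection". Section 6.10.1.1 says that subjects whose Day 84 result is at or below "ULN will collect an additional 24-hr urine sample for UFC on Day 92". Appendix 1 agrees: under footnote ^, those at or below "ULN should collect a repeat 24-hr UFC starting 7 days after R3/A3/ET", and under footnote h, those at or below "ULN will perform a 24-hr urine collection on Day 92". None of these four places mentions Day 79.

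**Steps at the exit visit.** Sections 7.3.4 (R3) and 7.4.4 (A3) do not set a third trigger. They say "A Day 92 24-hr UFC may or may not be needed" and refer to 7.5.1. Staff give the Day 92 instructions and book F1 only if the latest available UFC is at or below ULN. They withdraw the collection if Day 84 turns out above ULN. If the latest UFC is above ULN, the follow-up step is a telephone call 13 days later.

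**Type of F1 visit.** Section 6.10.1.1 adds: "The Day 79 result and the Day 84 result will be used to make the initial determinations" of whether follow-up is on site or by telephone. Section 3.1.5 says the latest result prevails when results disagree about that visit.

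**The concern.** The wording decides who has a scheduled safety test. Section 3.6 names adrenal suppression as a risk of ATR-101. For subjects on ATR-101 until exit (the ATR-101 arm and the additional open-label group), Day 92 is the first UFC off drug. Placebo subjects have been off drug since Day 57 and already have off-drug UFCs, so they lose less. The Day 92 result is also the stated condition, in 3.1.5, 6.10.1.1 and 7.5.2, for continuing ACTH and UFC checks every 2-4 weeks.

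A site reading 3.1.5 would not collect from a subject whose UFC was high on Day 79 and normal on Day 84. A site reading 7.5.1 would. A site working through the R3/A3 checklist would not have told the subject to collect, whichever rule it believed.

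**Working it through.** The protocol gives no figure to reproduce. The check compares the rules over all possible result patterns.

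**Inputs**
- Rule A (synopsis, 3.1.5): collect if Day 79 ≤ ULN and Day 84 ≤ ULN.
- Rule B (6.10.1.1, 7.5.1, footnotes ^ and h): collect if Day 84 ≤ ULN.
- Exit steps (7.3.4, 7.4.4): instruct if the latest available UFC ≤ ULN, then cancel if Day 84 > ULN.
- The Day 84 urine finishes on Day 85 and is handed in at R3/A3, so its result is not known then. For a completer the latest available result is Day 79 at best.

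**Comparison, with the Day 79 result back by the exit visit**

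| Day 79 | Day 84 | Rule A | Rule B | Instruction in force after R3/A3 |
|---|---|---|---|---|
| ≤ ULN | ≤ ULN | due | due | yes |
| ≤ ULN | > ULN | not due | not due | given, then cancelled |
| > ULN | > ULN | not due | not due | none |
| > ULN | ≤ ULN | **not due** | **due** | **none** |

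The rules differ in 1 of 4 patterns, and the exit steps leave a subject who is due under Rule B without instructions in that same pattern.

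**If the Day 79 result is not back by the exit visit.** The protocol gives no laboratory turnaround time. Section 3.1.3 allows that the Day 64/65 results may be unavailable at R2, which is 71 − 66 = 5 days after that collection ends. The Day 79 collection ends on Day 80 and exit is on Day 85, also 85 − 80 = 5 days. The instruction then depends on an earlier result:
- If that result is > ULN, every completer with Day 84 ≤ ULN leaves without instructions, including one whose Day 79 is also ≤ ULN.
- If it is ≤ ULN, no one who is due under Rule B is missed.

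**Delay if Day 92 is missed.** Under 7.5.2 the next UFC is arranged at the on-site F1, to be collected 2-4 weeks after the previous sample, here Day 84:
- 84 + 14 = Day 98 and 84 + 28 = Day 112.
- 98 − 92 = 6 days and 112 − 92 = 20 days later than Day 92.

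**Time available for a call-back.** Collections after R3/A3 have a ±7-day window (section 7 and Appendix 1):
- From a Day 85 exit to the target day: 92 − 85 = 7 days.
- To the end of the window: 92 + 7 = Day 99, and 99 − 85 = 14 days.

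**Early exits.** Subjects who leave before Day 84 appear to be covered by the R3/ET+7 label and by the Appendix 1 note that target days apply to full-duration completers. Even so, the condition in 7.5.1 names a Day 84 result that they do not have.

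**The case against.** The strongest reply is that the working instructions agree. Four places give Day 84 alone, and the only outlier is one word in a narrative section and its copy in the synopsis. No text forbids the collection. Section 7.5.1 covers the interval in which the Day 84 result returns, and it orders the collection. The latest-result rule points the same way. On this view only a reminder to telephone the subject is missing.

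Much of this stands. It shows which rule was probably meant and that a careful site could still get it right. It does not remove the contradiction. The latest-result rule settles only telephone or on-site follow-up on Day 98. Section 7.5.1 describes what subjects do, and this subject has been told nothing. Unlike 7.4.4, the above-ULN branch in 7.3.4 omits the word *available*, but a result still pending at the laboratory cannot be compared with ULN at the visit.

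Three further points limit the size of the problem:
- A Day 98 sample falls inside the ±7-day window for Day 92, so the shortest delay is within the plan's own tolerance.
- The on-site F1 still provides hormones, chemistry and an examination for adrenal insufficiency. A site that converts the call to an on-site visit has seen the Day 84 result and might then notice 7.5.1.
- After a Day 79 result above ULN the subject may start another agent once the exit visit is done (3.1.3, 3.1.4, 7.3.4, 7.4.4). A Day 92 result could then not be read as off drug.

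**Conclusion.** The point holds, as a minor correction to safety follow-up. The protocol gives two different triggers for the Day 92 UFC. They conflict for a completer with Day 79 above ULN and Day 84 at or below it, and the exit steps leave that subject without instructions. The collection is not prohibited. What is missing is the step that would make it happen.

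The effect is 1 of 4 result patterns and a next scheduled UFC 6 to 20 days after Day 92, counted in target days. The figure of 1 in 4 counts patterns, not subjects: the protocol does not show how often this pattern occurs, and no frequency is claimed. It assumes that Day 79 is back by exit and Day 84 is not. The delay assumes that the latest-result rule is applied, so that F1 is held on site. No efficacy endpoint uses the Day 92 result.

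**What to change.** 1. Delete *also* in the synopsis and section 3.1.5.
2. Use one trigger in the synopsis, 3.1.5, 6.10.1.1, 7.5.1 and Appendix 1 footnotes ^ and h: the last 24-hr UFC collected on or before R3/A3/ET (Day 84 for completers) is ≤ ULN. This also closes the wording gap for early exits.
3. Add one line to 7.3.4 and 7.4.4: if that result was pending at the visit and returns ≤ ULN, call the subject back to collect at R3/A3/ET+7, and change the telephone follow-up to an on-site F1. Keep the existing cancel step for a result > ULN.

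A call-back is enough, because the window leaves up to 14 days after a Day 85 exit. The alternative is to give provisional instructions to every completer whose Day 84 result is pending, and cancel them if it returns > ULN.

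The cost is protocol wording plus one telephone call for each completer with a high Day 79 whose Day 84 returns ≤ ULN. With provisional instructions instead, the cost is an occasional unneeded home collection. Neither option restores an off-drug reading in a subject who has already started another agent.

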3.2. Rationale for Study Design

This Phase 2 study will assess the ability of ATR-101 at various dose levels to suppress cortisol production in subjects with endogenous Cushing's syndrome. For subjects who meet randomization criteria, this study consists of an open-label dose-escalation period followed by a relatively brief (up to 4 weeks) placebo-controlled double-blind randomized withdrawal period

(where subjects are randomized in a 1:1 ratio either to continue to receive ATR-101 or matching placebo). This study design permits a placebo comparison with ATR-101 while minimizing the time during which subjects may experience elevated cortisol levels. Subjects who do not meet randomization criteria at the end of the open-label dose-escalation period will continue into an additional 4-week open-label dosing period, which permits assessment of efficacy following a longer duration of dosing with ATR-101.

The double-blinded withdrawal period of the study is randomized in order to minimize any bias in determining which subject receives ATR-101 or placebo. The study is double blinded so there is no bias introduced by knowledge of the treatment identity received by a subject in reporting the clinical findings. Double blinding also minimizes the bias in assessing treatment response measures that could be introduced by the Investigators had they known the treatment identity. The study is placebo-controlled in order to have a comparison group to help determine whether safety findings during the study are related to the study drug and also to provide a control rate for the assessment of efficacy. Stratification by baseline cortisol level allows for a balance of subjects with higher and lower levels in the treatment groups.

Based on toxicity investigations in preclinical species, previous clinical observations in PK and PD responses, expected bioavailability and safety demonstrated in a previous ATR-101 study in subjects with ACC, the doses of 250 mg BID, 500 mg BID and 1000 mg BID have been selected to evaluate the clinical effects of ATR-101 in subjects with Cushing's syndrome.

3.3. Study Duration

It is anticipated that the overall duration of the study per subject will range from approximately 16-22 weeks, depending upon the duration (if any) required for wash-out and the duration of follow-up.

3.4. Number of Subjects

Approximately 16 subjects are planned to be enrolled in this study. At enrollment, all eligible subjects will be assigned to one of two 24-hr UFC strata. Strata will be assigned according to baseline 24-hr UFC level: 1.3 to $< 4 \times \text{ULN}$ (Stratum I) and 4 to $10 \times \text{ULN}$ (Stratum II). Enrollment into a particular stratum may be limited to ensure the inclusion of subjects in both strata. The subject population will consist of adults with endogenous Cushing's syndrome with 24-hr UFC 1.3 to $10 \times \text{ULN}$.

The study will be conducted at approximately 14 sites in North America and the United Kingdom.

3.5. Treatment Assignment

There are a total of 3 dose levels for ATR-101 during the open-label dose-escalation period:

- 250 mg BID
- 500 mg BID
- 1000 mg BID

All enrolled subjects will be assigned to take the same starting dose of ATR-101, 250 mg BID. Dose escalation to the next higher dose of ATR-101, 500 mg BID, will occur at Visit T2. Further dose escalation to the next higher dose of ATR-101, 1000 mg BID, will occur at Visit T3.

A subject may enter the double-blind randomized withdrawal period if the mean Day 50/51 24-hr UFC is \leq ULN or \leq 50% relative to the baseline value. Such subjects will be randomized 1:1 to receive either ATR-101 at the same dose level on which they achieved the mean Day 50/51 24-hr UFC \leq ULN (or \leq 50% of their baseline value) (expected to be 1000 mg BID) or matching placebo in a double-blinded manner.

Subjects who do not meet any of the randomization criteria will enter the additional open-label dosing period and receive ATR-101 1000 mg BID.

3.6. Special Safety Topics

Preclinical studies at exposure levels much higher than those anticipated for this study have identified adrenal suppression with apoptotic histologic changes. The predicted exposures in this study are much lower; however, occurrence of such changes is a possibility. The investigative staff should be familiar with the warnings and precautions for ATR-101 as presented in the Investigator's Brochure.⁹

Adrenal suppression may present as adrenal insufficiency or as hypoaldosteronism. Subjects presenting with unexplained symptoms suggestive of adrenal insufficiency, such as fatigue, nausea, low blood pressure, characteristic electrolyte abnormalities (hyponatremia and hyperkalemia), etc., should be promptly evaluated for adrenal insufficiency and given replacement corticosteroids and/or mineralocorticoids as clinically indicated.

Subjects who develop unexplained persistent hyperkalemia and/or hyperchloremic metabolic acidosis should be evaluated for hypoaldosteronism. Subjects with confirmed hypoaldosteronism should receive mineralocorticoid replacement (e.g., fludrocortisone at a starting dose of 50-100 μ g/day) and should not be on any salt restrictions. Guidelines for the diagnosis and treatment of adrenal insufficiency and hypoaldosteronism may be found in [Appendix 6](#).¹²

